4.2.2 Secondary Outcome Measures

- #1: **Sustained T cell response.** Sustained change in CMI at 6 months will be assessed after receiving a second dose of booster vaccine post-immunization.
- #2: **Change in antibody response.** Antibody response will be measured by the change in VZV antibody concentration from pre-immunization to 1 month post-immunization. VZV antibody concentrations in serum samples will be measured using a commercially available ELISA kit (Abnova, Walnut, CA) according to the manufacturer's instructions. This quantitative VZV antibody concentration will be in addition to the one that may be needed to determine previous varicella infection for study eligibility.
- #3: **Sustained antibody response.** Sustained change in VZV antibody concentration at 6 months after receiving a second dose of booster vaccine post-immunization will be assessed.
- #4: Vaccine adverse effects. Patients will either receive phone calls from study personnel or be evaluated at clinic visits to ascertain vaccine-related adverse effects at months 1, 2, 3 (1 month post-immunization), and 8 (6 months post-immunization). Our study is underpowered to measure differences in adverse effects between groups. Adverse event data will be reported.
- #5: Change in UC disease activity. The SCCAI will be used to measure disease activity. It is a questionnaire with six subscore topics with scores defined by UC signs and symptoms from 0 to 4 for a

range of scores from 0 to 17. Total scores are interpreted as: Remission = score of 0 to 4 points, Mild Activity = score of 5 to 7 points, Moderate Activity = Score of 8 to 16 points, and Severe Activity = Score of > 16 points.

5 Study Design

The clinical trial will be a Phase IV multi-center non-randomized non-blinded observational study. As part of standard of care for this patient population and therefore outside of the study, each participant will be given two doses (0.5ml each) of the Shingrix vaccine, administered intramuscularly according to the following schedule: A first dose at Month 0 followed by a second dose administered anytime between 2 and 6 months later.

The study population will include adult outpatient subjects with UC. The study will compare the immunogenicity and VZV antibody concentrations in the participants who will be stratified into one of 4 arms (each containing 25 subjects) based on their medical regimen, which is also standard of care and will be established outside of the study:

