- Group A UC patients on tofacitinib monotherapy.
- Group B UC patients receiving anti-TNF monotherapy (adalimumab, golimumab, infliximab).
- Group C UC patients on an anti-TNF agent and a thiopurine (6-mercaptopurine, azathioprine).
- Group D UC patients on non-immunosuppressive therapy or 5-aminosalicylates.

As part of the actual study, 3 total blood samples will be collected. Samples will be collected at clinic visits at the time of enrollment, 1-month post-immunization, and 6 months post-immunization. Patients will also be asked to report change in their UC symptoms and any adverse effects to the vaccine at each clinic visit and follow-up phone calls.

6 Potential Risks and Benefits

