- #5 Follow up Phone Call 2 (approximately day 72): Subjects will receive a follow-up phone call to identify any adverse effects including fevers or chills, rash, and visits to the emergency room or to their primary care physicians. They will also be reminded about their follow up visit.
- #6 Follow up Visit 4 (approximately day 90): Subjects will complete a SCCAI questionnaire, and information will be collected to identify any adverse effects including fevers or chills, rash, and visits to

Version 1.7 06/22/2023

the emergency room or to their primary care physician. A blood sample of approximately 20mL (4 tablespoons) will then be obtained.

#7 - Follow up Visit 5 (approximately day 240): Subjects will complete a SCCAI questionnaire, and information will be collected to identify any adverse effects including fevers or chills, rash, and visits to the emergency room or to their primary care physician. A blood sample of approximately 20mL (4 tablespoons) will then be obtained.

The entire procedure will be identically performed at the additional sites outside of BMC. The total study duration will be about 2 years, and the subjects' duration of participation will range from 8 to 12 months, depending on when the 2nd vaccine dose is administered.

Participants will receive a total of \$50 in the form of reimbursement gift cards for their participation. A \$20 gift card will be given at the time of enrollment, and a \$30 gift card will be given at the 1-month post-immunization visit (follow-up visit 4).

All standard-of-care testing and procedures will be billed to the patient/patient's insurance. All initial research visits will be conducted as part of an already scheduled visit that the patient would be attending regardless of study participation; thus, the patient (or the patient's insurance) would cover the cost of this. At this visit, the patient will be vaccinated with a clinically indicated vaccine(s) that would be part of standard preventative care and have blood drawn. Patients with IBD generally have routine blood testing as part of their regular care. Given this, phlebotomy will be covered by the patient or their insurance, with the exception of the cost of the blood draws specifically for the research study (at follow up visits) which will be covered by research funding. The vaccine will be purchased with funding from Pfizer and be provided to subjects at no cost.

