11.6 Sample Size Determination

We will recruit a total of 100 subjects, anticipating 25 subjects per study arm. Assuming an attrition rate of 20%, our goal final sample size is 80 subjects, with 20 subjects in each arm.

Power calculations revealed that >200 patients per study arm would be needed to estimate small differences in efficacy, assuming a 10% difference between tofacitinib monotherapy patients and non-immunosuppressed IBD patients for instance. Since there are no previous data on vaccine responses to HZ in IBD patients from which we can calculate power estimates, sample size has been determined by feasibility of recruitment at various sites. Our goal is to perform exploratory data analyses and derive estimates of vaccine response results in this population to power future studies.

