11.7 Statistical Methods

Summary statistics including the mean, median, SD and range will be presented for continuous variables and N (%) will be presented for categorical variables, overall and by IBD group. Comparisons across groups on baseline demographic and clinical characteristics will be performed using ANOVA for continuous variables and the chi-squared test for categorical variables. Any comparison across groups significant at the p< 0.1 level will be considered for a multivariable-adjusted model for the primary outcome.

For the primary outcome of percent change in cell-mediated immunity from baseline to one-month post-immunization, we will first compare the tofacitinib alone group (Group A) to the non-immunosuppressive group (Group D) using a contrast statement as part of an ANOVA model. Comparisons of Group A with Groups B and C will use the same methodology. The same methodology will be used to compare the secondary outcomes among the four IBD groups in a similar manner. Any imbalances in baseline characteristics will be incorporated into a multivariable regression model to determine the adjusted differences between groups.

Incidence of adverse events will also be compared between groups using the chi-squared or Fisher's Exact test, as appropriate. A value of p< 0.05 is considered statistically significant, except where otherwise noted.

12 Ethics/Protection of Human Subjects

This study is to be conducted according to applicable US federal regulations and institutional policies (which are based in federal regulations, guidance, and ICH Good Clinical Practice guidelines).

This protocol and any amendments will be submitted to the Boston Medical Center and Boston University Medical Campus IRB, for formal approval of the study conduct. The decision of the IRB concerning the conduct of the study will be made in writing to the investigator. A copy of the initial IRB approval letter will be provided to the sponsor before commencement of this study.

All subjects for this study will be provided a consent form describing this study and providing sufficient information for subjects to make an informed decision about their participation in this study. The consent form will be submitted with the protocol for review and approval by the IRB. The consent of a subject, using the IRB-approved consent form, must be obtained before that subject is submitted to any study procedure. Consent will be documented as required by the IRB.

13 Literature References

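### The 6-month CMI and antibody contrasts use only participants sampled at 6 months; one repeated-measures model per marker would use the 1-month data too, a modest gain at little cost

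*Combined protocol and SAP*

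**What the plan says.** Section 11.7 sets the primary analysis: "For the primary outcome of percent change in cell-mediated immunity from baseline to one-month post-immunization", Group A is compared with Group D "using a contrast statement as part of an ANOVA model", and then with Groups B and C in the same way. For the other outcomes: "The same methodology will be used to compare the secondary outcomes among the four IBD groups in a similar manner".

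Section 4.2.2 lists two 6-month outcomes among these: "Sustained change in CMI at 6 months will be assessed after receiving a second dose of booster vaccine post-immunization" and "Sustained change in VZV antibody concentration at 6 months after receiving a second dose of booster vaccine post-immunization will be assessed". Section 5 plans three samples per person: "Samples will be collected at clinic visits at the time of enrollment, 1-month post-immunization, and 6 months post-immunization".

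Section 11.6 gives the expected loss: "Assuming an attrition rate of 20%, our goal final sample size is 80 subjects, with 20 subjects in each arm". It gives neither the timing of the loss nor separate rates by arm.

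The only text on missing data is a rule in section 11.3 for completing case report forms. Section 11.7 does plan a regression adjusted for baseline characteristics that are out of balance. It names no repeated-measures model, imputation, analysis population or sensitivity analysis for missing visits, and nothing brings the 1-month response into the 6-month analysis.

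**The concern.** The plan does not use the term complete case, but an ANOVA on change at a single time point can include only people measured at that time point. With no other rule stated, someone who gives the baseline and 1-month samples and then leaves is absent from the 6-month contrasts. Their 1-month value would help to predict the missing one.

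Two things are at stake. One is precision. The other is bias, if the people who leave differ in response from those who stay, and differ in one arm more than in another. The arms are non-randomized treatment regimens, and section 4.1 itself describes them as different: aminosalicylates are for mild-to-moderate disease, while tofacitinib patients have probably failed a biologic. Two of the four hypotheses in section 11.5 concern 6 months, and section 11.6 says that the estimates are meant to power later studies.

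**Working it through.** **Inputs from the documents.** 100 enrolled, 25 per arm, 20% attrition (section 11.6); samples at baseline, 1 month and 6 months (section 5).

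**Assumptions, because the documents give no figures.** SD of the response = 1; correlation ρ between the 1- and 6-month responses from 0.3 to 0.9; the dropout mechanisms listed below.

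**1. The plan's own figure.** 100 × 0.8 = 80 and 25 × 0.8 = 20 per arm. This reproduces exactly. Up to 25 − 20 = 5 people per arm, 20 in all, could have a 1-month but no 6-month sample.

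**2. Precision.** With n1 per arm at 1 month and n6 = 20 at 6 months, the variance of a joint-model contrast relative to the completers-only one is 1 − ρ²(1 − n6/n1). The completers-only standard error is √(2/20) = 0.316 SD. If all loss follows the 1-month draw, n1 = 25 and the ratio is 1 − 0.2ρ²:

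| ρ | Variance ratio | Effective n per arm | SE, joint model | Reduction in SE |
|---|---|---|---|---|
| 0.3 | 0.982 | 20.4 | 0.313 | 0.9% |
| 0.5 | 0.950 | 21.1 | 0.308 | 2.5% |
| 0.7 | 0.902 | 22.2 | 0.300 | 5.0% |
| 0.9 | 0.838 | 23.9 | 0.290 | 8.5% |

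With n1 = 22 the effective n is only 20.2 to 21.6. With n1 = 20 (all loss before the 1-month draw) the ratio is 1 and nothing is gained.

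**3. Bias of the 6-month contrast.** Simulated with 25 per arm, 20% lost after the 1-month sample and a true difference of 0:

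| Dropout mechanism | Completers-only bias (SD) | Joint-model bias (SD) |
|---|---|---|
| Unrelated to response | 0 | 0 |
| Related to response in the same way in both arms | 0 | 0 |
| One arm, driven by severity (correlation −0.3 with response), ρ 0.5-0.7 | 0.04-0.06 | 0.01-0.03 |
| One arm, low 1-month responders leave, logistic slope 0.7 / 1.2, ρ = 0.5 | 0.060 / 0.102 | at most 0.005 |
| The same, ρ = 0.7 | 0.089 / 0.143 | at most 0.005 |
| One arm, probit slope 1, ρ = 0.5 / 0.7 / 0.9 | 0.12 / 0.18 / 0.22 | about 0 |

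In the last row the type I error of the completers-only test is 0.067, 0.088 and 0.107; with random dropout it is 0.05.

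The severity row can be checked by hand. The logistic slopes shift the completers' mean of the driving variable by 0.060/0.5 = 0.12 SD and 0.102/0.5 = 0.20 SD. Multiplying by 0.3 gives 0.04 and 0.06. A joint model without a severity term leaves the fraction 1 − ρ: from 0.04 × 0.3 ≈ 0.01 to 0.06 × 0.5 = 0.03.

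**The case against.** The strongest reply is that little is shown to be wrong, and much of it stands.

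- **Bias needs more than informative dropout.** A reader might infer that the completers-only contrast is sound only if dropout is unrelated to response. That is too strong: if the relation is the same in both arms, the bias cancels. Unequal dropout rates alone do not create bias either.
- **The mechanism is indirect.** Under section 9 samples are frozen and released to the testing co-investigator once enrolment is finished, and nothing says that assay results reach participants. Attendance can hardly respond to the 1-month value itself. A link through disease severity is more natural, and it gives the smallest non-zero biases in the table.
- **The timing is unknown.** A reader might infer late loss because the last gift card is given at the 1-month visit. The documents do not say so, and loss before the second dose, which may be as late as day 180, is just as possible.
- **Some protection is already planned.** If the adjusted regression in section 11.7 covers the 6-month outcomes and includes baseline SCCAI, it would remove part of any severity-driven bias. Its reach is arguable, since the screening rule for covariates mentions only the primary outcome.
- **The outcomes are secondary** in a study sized by feasibility and described as exploratory.

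What remains is that the stated method leaves out collected, informative data when a better model costs almost nothing. The exploratory aim does not remove the point, because the estimates are to be carried into later sample-size calculations.

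**Conclusion.** The point holds as a cheap, conditional improvement to the secondary 6-month analyses. The precision gain is 0 to about 8% of the standard error, depending on when people leave and on a correlation that the documents do not give. Under the assumed one-arm mechanisms the bias is about 0.04-0.22 SD, smaller than the standard error of about 0.32 SD; it is zero when dropout is unrelated to response or related to it in the same way in both arms.

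A reader might go further and conclude that the 6-month results will be biased. The documents do not support that: they assume an equal 20% loss in every arm and describe no mechanism. Harsher assumptions give more (up to 0.28 SD for a steeper one-arm dependence, and 0.25-0.45 SD if opposite kinds of responder leave the two arms), but nothing in the plan points to them. Non-randomized arms make differential dropout possible; they do not establish it. The primary 1-month contrast is barely affected.

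**What to change.** In section 11.7, for CMI and for antibody, replace the separate ANOVAs with one repeated-measures model per marker on log values:

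- terms for group, visit, group × visit, log baseline and log baseline × visit;
- the baseline characteristics that the plan already intends to adjust for, such as baseline SCCAI;
- an unstructured covariance over the two post-baseline visits;
- everyone with at least one post-baseline value included.

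Read the A-vs-D, A-vs-B and A-vs-C contrasts at 1 and 6 months from this model. Report losses by group, timing and reason. Keep the completers-only ANOVA as a sensitivity analysis: it shows how far the result depends on the joint modelling, although it does not test the missing-at-random assumption.

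The cost is wording and a little programming, with no new visits, samples or participants. The model relies on data being missing at random given the modelled values, and on a covariance estimated from about 80 to 100 people. The log scale is a separable choice; it needs a stated rule for zero counts and for wells reported as above 300 spots.

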6.2 Potential Benefits

There are no direct benefits to subjects from participating in the study.

Societal benefits include providing data on the effectiveness of the Shingrix vaccine in patients on immunosuppressants. The data from this pilot study may be used to guide larger more powered studies in the future. The data from our study may also provide reassurance to patients and providers that that Shingrix is safe in a real-world setting for patients on immunosuppressants.

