10.1 Definitions

The following definitions will be used in the assessment of safety:

Adverse Event (AE) is any untoward or unfavorable medical occurrence in a human subject, including any abnormal sign (for example, abnormal physical exam or laboratory finding), symptom, or disease,

temporally associated with the subject's participation in the research, whether or not considered related to the subject's participation in the research.

Serious Adverse Event (SAE) is any adverse event that

- (1) results in death;
- (2) is life-threatening;
- (3) results in inpatient hospitalization or prolongation of existing hospitalization;
- (4) results in a persistent or significant disability/incapacity;
- (5) results in a congenital anomaly/birth defect; or
- (6) based upon appropriate medical judgment, may jeopardize the subject's health and may require medical or surgical intervention to prevent one of the other outcomes listed in this definition (examples of such events include allergic bronchospasm requiring intensive treatment in the emergency room or at home, blood dyscrasias or convulsions that do not result in inpatient hospitalization, or the development of drug dependency or drug abuse).

Life-threatening means that the event places the subject at immediate risk of death from the event as it occurred.

Unanticipated Problem is defined as an event, experience or outcome that meets **all three** of the following criteria:

- is unexpected; AND
- is related or possibly related to participation in the research; AND
- suggests that the research places subjects or others at a greater risk of harm (including physical, psychological, economic, or social harm) than was previously known or recognized.

Possibly related means there is a reasonable possibility that the incident, experience, or outcome may have been caused by the procedures involved in the research

Unexpected means the nature, severity, or frequency of the event is not consistent with either:

- the known or foreseeable risk of adverse events associated with the procedures involved in the
 research that are described in (a) the protocol—related documents, such as the IRB-approved
 research protocol, any applicable investigator brochure, and the current IRB-approved informed
 consent document, and (b) other relevant sources of information, such as product labeling and
 package inserts; or

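### Adverse-event incidence is compared between arms only by significance tests that the protocol itself calls underpowered, with no interval planned and no stated event set

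*Combined protocol and SAP*

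**What the plan says.** Section 11.7 (Statistical Methods) gives one sentence to the adverse-event comparison: "Incidence of adverse events will also be compared between groups using the chi-squared or Fisher's Exact test, as appropriate". The next sentence sets the threshold: "A value of p< 0.05 is considered statistically significant, except where otherwise noted". No exception is noted for adverse events. The section does not say which contrasts are tested (four-group or pairwise), which events count, or how a non-significant result is to be read. It does plan counts and percentages for categorical variables, overall and by group, but no confidence intervals.

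Section 4.2.2, outcome #4, concerns vaccine-related adverse effects and ends: "Our study is underpowered to measure differences in adverse effects between groups. Adverse event data will be reported". The secondary objectives in Section 4.1 also refer to vaccine-related events. Section 10.1 defines an adverse event more widely, as one "temporally associated with the subject's participation in the research, whether or not considered related to the subject's participation in the research".

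Section 6.2 says the data "may also provide reassurance to patients and providers that that Shingrix is safe in a real-world setting". On numbers, Section 11.6 states: "We will recruit a total of 100 subjects, anticipating 25 subjects per study arm", and then: "Assuming an attrition rate of 20%, our goal final sample size is 80 subjects, with 20 subjects in each arm".

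**The concern.** Two sections point in different directions. Section 4.2.2 concedes that the study is too small for between-arm differences in adverse effects and says only that the data will be reported. Section 11.7 then makes a test of those differences the only planned comparison. A p-value from such a test does not show how large a difference, or how high a reaction rate, remains compatible with the data. An interval would.

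The event set is also open. If 11.7 means outcome #4, it counts vaccine-related effects. If it uses the term as defined in 10.1, it counts events of any cause over 8 to 12 months of participation. UC and drug events could then differ by regimen for reasons unrelated to the vaccine.

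Finally, the test addresses a different question from the safety objective. Every subject is vaccinated, and the arms are defined by UC treatment without randomization. A between-arm test asks whether event rates vary with background therapy. It does not estimate how often reactions occur on any regimen.

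**Working it through.** **Inputs from the plan.** 25 subjects per arm enrolled and 20 after attrition (11.6); significance level 0.05 (11.7); published reaction rates for the vaccine, such as fever 20.5% and fatigue 44.5% (6.1).

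**Assumptions.** Tests are two-sided. The comparison rates are illustrative: 20% is close to the fever rate in 6.1, and 40% is a doubling of it.

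**1. The plan's own figures.** There is no power figure for adverse events. The only one concerns efficacy: "Power calculations revealed that >200 patients per study arm would be needed to estimate small differences in efficacy, assuming a 10% difference". Taking 90% against 80% as an assumption (Section 4.1 cites a response above 90% in healthy people), with 80% power and mean rate 0.85:

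n = [1.96·√(2·0.85·0.15) + 0.842·√(0.90·0.10 + 0.80·0.20)]² / 0.10² = (0.990 + 0.421)² / 0.01 ≈ 199 per arm, or 219 with continuity correction.

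The stated figure is reproduced. The attrition arithmetic also holds: 100 × 0.8 = 80, and 80 / 4 = 20 per arm.

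**2. The same question for adverse events.** For a 10-point excess over the reaction rates in 6.1, the same formula gives 221 to 392 per arm (298 for fever).

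**3. Power at the planned size.** Power is the sum, over all pairs of event counts (x, y), of the binomial probability of each pair for which the test gives p < 0.05. The plan allows chi-squared or Fisher. The last column uses chi-squared when all expected counts are at least 5 and Fisher otherwise.

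| Assumed rates | n per arm | Fisher alone | Chi-squared where counts allow |
|---|---|---|---|
| 20% vs 40% | 20 | 19% | 28% |
| 20% vs 40% | 25 | 23% | 35% |
| 20% vs 50% | 20 | 41% | 53% |
| 20% vs 50% | 25 | 51% | 64% |
| 20% vs 60% | 20 | 65% | 75% |
| 20% vs 60% | 25 | 79% | 87% |
| 5% vs 15% | 25 | 7% | 8% |

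At 20% vs 40% the expected events per arm are (4 + 8)/2 = 6 with 20 subjects and (5 + 10)/2 = 7.5 with 25, so chi-squared would usually apply. A four-arm chi-squared test with one arm at 40% and three at 20% has power 29% (20 per arm) or 35% (25 per arm), by simulation.

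For increases from the systemic-reaction rates in 6.1, 80% power needs a difference of about 41 to 49 points at 20 per arm, or 37 to 41 points at 25. For rare events Fisher needs 5/20 against 0/20 (p = 0.047), or 6/25 against 0/25 (p = 0.022), to fall below 0.05.

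**4. What an interval would show.** With zero events, the exact two-sided 95% upper limit is 1 − 0.025^(1/n): 16.8% for n = 20, 13.7% for n = 25, 4.5% for n = 80 and 3.6% for n = 100. With identical observed rates, the Newcombe 95% interval for the difference is about ±25 points for 4/20 vs 4/20 and about ±22 points for 5/25 vs 5/25.

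**The case against.** The protocol discloses the limitation beside the outcome, calls its analyses exploratory (11.6), and already plans percentages by group. This is a secondary outcome of a pilot. All of that stands and keeps the point modest. It does not supply the missing interval, define the event set, or say how a non-significant test is to be read.

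Four stronger readings are tempting but not supported:

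- **A reader might infer that non-significant tests will be presented as evidence of vaccine safety.** No section says so. The reassurance sentence in 6.2 is tentative, sits under potential benefits and is tied to no test.
- **A reader might infer that the study cannot detect any difference, or that non-significance is close to certain.** The protocol says underpowered, and differences of 40 points or so are within reach. At 20% vs 40% the chance of non-significance runs from 65% (1 − 0.35) to 81% (1 − 0.19). Fisher-only figures are pessimistic, because 11.7 also allows chi-squared.
- **A reader might infer that 11.7 tests all-cause events.** The wording is compatible with 10.1, but outcome #4 uses the terms adverse effects and adverse event data side by side. The documents support only that the event set is unspecified.
- **A reader might infer that significance tests must be removed.** That is a preference. A descriptive p-value beside an interval does no harm if it is labelled as such.

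**Conclusion.** The point holds as an analysis and reporting gap. Section 11.7 relies on tests that 4.2.2 calls underpowered, plans no interval, and leaves the event set undefined. For a doubling from 20% to 40%, power is between 19% and 35% across the two sample sizes, the pairwise tests and the four-arm test. A non-significant result is therefore likely and would not distinguish similar rates from materially different ones. An arm with no events remains compatible with a true rate of roughly one in seven (25 subjects) or one in six (20).

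These powers rest on two-sided 0.05, equal arms of 20 or 25, and assumed event rates; the plan gives none by arm. The interval limits do not depend on assumed rates. The structural point, that all arms are vaccinated and not randomized, needs no calculation. The change is worth making but modest in weight: the outcome is secondary and its limitation is already disclosed.

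**What to change.** Replace the adverse-event sentence in 11.7 with text to this effect:

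*For each arm and for all arms pooled, the proportion of subjects with a vaccine-related adverse effect (outcome #4) and, separately, the proportion with any adverse event as defined in Section 10.1 will be reported with exact (Clopper-Pearson) 95% confidence intervals. Between-arm differences will be shown as risk differences with 95% confidence intervals. Any p-value is descriptive, and a non-significant result will not be interpreted as similar safety.*

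Do not add a fixed onset window, such as 14 days, on the strength of the phone-call schedule alone. The day-14 call falls about 7 days after a first dose given at the day-7 visit, and the day-72 call precedes a second dose given as late as day 180. The sponsor should set any window from what the diary card listed in 11.3 and the planned contacts actually capture.

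The cost is revised wording and a few more table columns. The trade-off is less emphasis on p-values. Without an onset window, no new data collection is needed, and the change fits the estimation goal stated in 11.6.
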